This will be a randomized, assessor and participant-blinded study. Adult patients (aged 20 years or older) scheduled for surgical treatment for hip fracture with American Society of Anesthesiologists (ASA) physical status I-III will be assessed for eligibility to participate the study. The exclusion criteria includes: allergy to local anesthetics, pregnancy, inability to understand and use the numerical rating scale (NRS 0-10, 0: no pain, 10: worst pain imaginable) after instruction, chronic use of opioids, coagulopathy, neuropathy or severe diabetic mellitus. If the patients give his /her informed consents, his/her baseline demographic data (gender, age, height, and body weight) and types of hip fracture will be recorded. Participants will be randomly allocated into either FIC block or PENG block by using the website RESEARCH RANDOMIZER (<https://www.randomizer.org>). One of the two anesthesiologists experienced in performed the FIC and PENG blocks will perform the nerve blocks. Only the anesthesiologist performing the nerve block and his assistant will be aware of which nerve block the participant received immediately

before performing nerve block by opening a sealed envelope. The assessors, in-charge anesthesiologists and nurse anesthetists, operation room personnel, surgeons and study participants will be all blinded to the randomization. The participants are unlikely to know which nerve block they receive because the needle insertion sites and needle trajectories of these two nerve blocks are quite close to each other.

On arrival of the operating theater, all participants will be sent to the nerve block area, where continuous electrocardiogram (ECG), pulse oximetry, and non-invasive intermittent blood pressure monitoring will be applied and an intravenous line will be established. Before any intervention, pain at rest and during the fractured lower limb being passively internal rotated in extension to neutral position from its usual externally rotated deformity by assessors will be assessed using NRS. If the participant cannot tolerate passive internal rotation of his/her fractured limb due to pain, impossibility to perform the test will be recorded as well as the worst NRS score during these attempts. The same assessment will be performed every 10 mins for until 30 mins after completion of the nerve block. Then the patient will be sent to the operation room, where spinal anesthesia will be performed for the surgery.

Procedures of the nerve blocks

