The primary outcome of this study is the pain measurement at rest and during the fractured limb being passively internally rotated 30 mins after nerve block. The secondary outcomes includes the pain measurement during positioning for spinal anesthesia (from supine to lateral decubitus with flexion of the healthy hip), pain measurement at 6, 12, and 24 hours after operation, the time spending for performing spinal anesthesia (defined as starting of positioning maneuver to removal of spinal needle), quality of position for spinal anesthesia (characterized as unsatisfied, satisfied, good, and excellent by the anesthesiologists performing the spinal anesthesia), the time interval between the end of operation and pain first perceived by the patient, the time interval between the end of operation and the first request for rescue analgesics, total consumption of rescue analgesics within 24 hours after the operation, the time interval between the end of operation and the first time the patient can ambulate with assistance after operation, the time spending for nerve block (defined as from contact of skin by the ultrasound transducer to removal of the needle), and satisfaction of the patient regarding preoperative analgesia from nerve block (very good, good, adequate, poor, very poor) inquired on the 1st postoperative day.

Statistics

Based on a previous study, the standard deviation of pain score after FIC block was 2.4¹⁰. Assuming the minimal clinically important difference in NRS score is 1.5, 44 patients in each group are required to achieve a power of 80% and a level of significance of 5% (two sided). One hundred eligible patients (50 patients in each group) will be enrolled in the study after informed consents are obtained. The data of normal distribution will be analyzed with independent *t*-test, otherwise Mann-Whitney U test will be used for analyses. Categorical data will be analyzed using χ^2 test or Fisher's exact test. $P < 0.05$ will be considered statistically significant.

There is no conflict of interest.

Reference

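### The primary analysis ignores the pre-block pain scores the trial already collects, and leaves the choice of test to an undefined normality check

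*Combined protocol and SAP*

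**What the plan says.** The Methods section schedules a baseline assessment: "Before any intervention, pain at rest and during the fractured lower limb being passively internal rotated in extension to neutral position" is scored on the NRS. It continues: "The same assessment will be performed every 10 mins for until 30 mins after completion of the nerve block". If a participant cannot tolerate the rotation, that fact is recorded together with the worst score reached in the attempts, so a number is still planned.

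Under Outcome measurements, the primary outcome is the "pain measurement at rest and during the fractured limb being passively internally rotated 30 mins after nerve block". Each primary score therefore has a matching pre-block value on the same scale.

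The Statistics section gives the whole analysis of numerical outcomes in one sentence: "The data of normal distribution will be analyzed with independent" t-tests, "otherwise Mann-Whitney U test will be used for analyses". Categorical data go to chi-square or Fisher tests. No covariate, change score, regression or repeated-measures model is named, and nothing says how normality is to be judged. Allocation is by a randomisation website, with no stratification described.

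The sample size takes an SD of 2.4 from a previous study of fascia iliaca block. "Assuming the minimal clinically important difference in NRS score is 1.5", the plan arrives at 44 per group for 80% power at a two-sided 5% level, and then: "One hundred eligible patients (50 patients in each group) will be enrolled".

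**The concern.** Pre-block pain is likely to predict pain half an hour later to some degree. Where it does, a comparison of the 30-minute scores alone leaves explainable variation in the error term, and the confidence interval is wider than it need be. Any chance difference between the arms in pre-block pain also passes into the 30-minute comparison. Unstratified allocation does nothing to limit such a difference. If adjustment is added only after an imbalance is seen, it is open to the charge of having been chosen for its result, so it has to be written down beforehand.

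The normality rule adds a second problem. An integer score on 0-10 after an effective block is often skewed or piled at low values, so the plan may well end in Mann-Whitney. That test takes no covariate and does not estimate a mean difference, yet the trial is sized on a mean difference of 1.5. As written, neither the primary test nor the effect measure is fixed before the data are seen.

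**Working it through.** **Inputs.** SD 2.4, difference 1.5, two-sided 5%, 44 required and 50 enrolled per group: all from the Statistics section. The correlation r between baseline and 30-minute NRS is not in the documents. It is assumed, with 0.3 to 0.7 as the main range and 0.2 as a lower check. The SD of 2.4 is applied to both primary scores and, in step 3, to baseline; these too are assumptions.

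**1. The plan's own figure.** The normal approximation gives n = 2 × [2.4 × (1.960 + 0.842) / 1.5]² = 40.2, so 41 per group. The exact t-test calculation gives 41.17, so 42. Dividing 41.17 by the Mann-Whitney efficiency 3/π (0.955) gives 43.1, so 44. The stated 44 is thus reproduced within two patients by the t-test, and exactly with the Mann-Whitney correction. Power at 44 per group is 82.6% by t-test.

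**2. Effect of adjustment at 50 per group.** Unadjusted, the standardised difference is 1.5/2.4 = 0.625, and the noncentrality is 0.625 × √(50/2) = 3.125. With ANCOVA:

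- residual SD = 2.4 × √(1 − r²)
- standardised difference = 0.625/√(1 − r²)
- equivalent group size = 50/(1 − r²)
- 95% CI half-width = 1.984 × residual SD × √(2/50)

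| r (assumed) | Residual SD | Variance removed | Power, 5% level | n per group for 80% power | CI half-width | Equivalent n per group |
|---|---|---|---|---|---|---|
| unadjusted | 2.40 | 0% | 87.2% | 42 | 0.95 | 50 |
| 0.2 | 2.35 | 4% | 88.5% | 40 | 0.93 | 52.1 |
| 0.3 | 2.29 | 9% | 90.0% | 38 | 0.91 | 54.9 |
| 0.5 | 2.08 | 25% | 94.7% | 32 | 0.83 | 66.7 |
| 0.7 | 1.71 | 49% | 99.1% | 22 | 0.68 | 98.0 |

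If each of the two primary scores were tested at 2.5%, which the plan does not specify, power would be 80.1% unadjusted and 83.9%, 90.7% and 98.1% at r = 0.3, 0.5 and 0.7.

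**3. Chance imbalance.** With baseline SD 2.4, the difference in mean baseline NRS has standard error 2.4 × √(2/50) = 0.48, so its 95% range is ±1.96 × 0.48 = ±0.94. With equal SDs at both times, an imbalance of 0.94 moves the unadjusted 30-minute difference by r × 0.94. That is 0.28, 0.47 or 0.66 points at r = 0.3, 0.5 or 0.7, against a target of 1.5.

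This was checked in 20,000 simulated bivariate-normal trials for each r, with 50 per arm and no true effect. Over all trials both tests reject about 5% of the time. Among trials with imbalance beyond ±0.94, the unadjusted t-test rejects in about 10%, 20% and 33%, and ANCOVA in about 5%.

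**4. The normality gate.** Scores were simulated with underlying mean 2 or 3 and SD 2.4, rounded and cut off at 0 and 10, with 50 per arm and no true effect. A Shapiro-Wilk test at 5% in each arm sent at least 99% of trials to Mann-Whitney. The type I error of the gated procedure stayed near 5%.

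**The case against.** The strongest reply is that nothing here is invalid. Under randomisation the unadjusted comparison is unbiased over allocations and holds its error rate, as step 3 shows. The 10% to 33% rates apply only to the roughly one trial in twenty with imbalance beyond the 95% range. The trial also meets its 80% target without adjustment: 87.2% by t-test at 50 per group, and about 85.6% allowing for Mann-Whitney. All of that stands, and it is why this is an improvement the sponsor should make and not a fault that undermines the trial.

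The size of the gain rests on a correlation the documents do not supply. At r = 0.2 power rises by only about one point. This also stands, but the cost is a single degree of freedom, so there is no material loss if r proves low.

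Normal-theory power sits awkwardly with the expectation of skewed scores. Simulations with rounded, bounded scores bear this out in part. One gave about 87%, 92% and 98% for ANCOVA at r = 0.3, 0.5 and 0.7, against 85-86% unadjusted. A setting with stronger floor effects gave about 88% and 93% at r = 0.5 and 0.7, against 82%. The power levels in the table are therefore somewhat optimistic, but the advantage of adjusting remains.

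The gate is written in advance and does not inflate type I error, and the 44 per group is consistent with having allowed for Mann-Whitney, although the plan does not say so. Such an allowance would cover that test's power. It would not supply a mean difference to set against 1.5, nor the missing normality criterion.

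Finally, some baseline rotation scores will come from an incomplete movement. They remain usable as covariates because they are taken before the block, but the SAP should say how they enter the model.

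**Conclusion.** The concern holds. Both baseline scores are collected, no planned test uses them, and the primary test depends on a normality judgement with no stated criterion. The consequence is lost precision and exposure to chance imbalance in the trial as realised; there is no systematic bias and no shortfall against the stated power. With r assumed between 0.3 and 0.7, the analysis forgoes a 9% to 49% reduction in residual variance, which is equivalent to about 5 to 48 extra patients per group. The gain is material at r of 0.5 or above and small below 0.3. The omission itself is certain from the text. Its size depends on r, on an SD of 2.4 for both scores and, for the power levels, on approximate normality.

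**What to change.** In the Statistics section, make the primary analysis an ANCOVA of the 30-minute NRS on arm and the matching baseline NRS: rest on rest, rotation on rotation. Report each adjusted mean difference with its 95% CI and read it against the 1.5-point minimal clinically important difference. Remove the normality gate for the primary outcome and keep Mann-Whitney as a sensitivity analysis. Add a sentence stating that, where rotation was not tolerated, the recorded worst score is the value used at that time point, or name another rule.

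The cost is SAP wording and one degree of freedom. The data are already scheduled, so there are no extra patients, visits or measurements. The change should be made before anyone sees outcome data by arm.
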